## 7 Discontinuation of Study Intervention and Participant Discontinuation/Withdrawal

### 7.1 Discontinuation of Study Intervention

Not applicable.

### 7.2 Participant Discontinuation/Withdrawal from the Study

This is a single-dose treatment study. If a participant withdraws prior to administration of the study treatment, the End-of-Study visit will be performed and no attempts will be made to collect additional data. No further evaluations will be performed, except for safety purpose when applicable.

- A participant may withdraw from the study at any time, upon request of participant's parent or guardian/legally authorized representative (i.e., withdrawal of consent) or if the child communicates (verbally or opposing resistance) that he/she is unwilling to continue, and without giving a reason. However, the reason should be obtained when it is possible to do so, and then the reason should be reported in the appropriate Case Report Form.
- The participant may be withdrawn by the Investigator due to participation in another clinical study.
- The participant may be withdrawn at any time at the discretion of the Investigator for safety, behavioral, compliance, or administrative reasons.
- The participant may be withdrawn if lost to follow-up.
- If a participant withdraws from the study, no further evaluations should be performed, and no attempts should be made to collect additional data, with the exception of safety data, which should still be collected if possible, but not captured in the database.
- If a participant is withdrawn from the study because of a treatment-limiting AE, thorough efforts should be made to clearly document the outcome.
- Data obtained prior to a participant's withdrawal will still be included in the efficacy and safety analysis.
- Participants withdrawn from the study will not be replaced.

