##### Secondary outcome: Acceptability of the Study Intervention

Reaction to Study Intervention administration (e.g., spitting, crying) will be recorded, to describe tolerability as assessed by nurse/site staff for all children enrolled in the study.

The palatability assessment will use a human gustatory sensation test (100-mm VAS) scoring modified by the incorporation of a 3-point facial hedonic scale for all children 5 and 6 years of age enrolled in the study.

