8.2 Definition of Analysis Populations and Subgroups

Screening Analysis Population (SCR)

The Screening analysis population includes all participants who signed the informed consent.

Intention-to-Treat (ITT)

For the purposes of this trial the ITT analysis set described in the protocol and the safety analysis set described below are considered equivalent. For this reason, the safety analysis set will be utilized for ITT and safety analysis purposes.

Modified ITT Analysis Population (mITT)

The modified ITT (mITT) analysis population will include all enrolled participants who receive one dose of treatment and have baseline measurement. Children who require malaria treatment after enrollment in the study will not be included in the mITT population. The primary analysis of this study will be performed on the mITT population.

Per Protocol Analysis Population (PP)

Per-protocol (PP) Analysis population includes all participants who are in the mITT population and have one post baseline measurement for Cohorts 1, 2, 3 and 4a, and two post baseline measurements for Cohort 4b, without any clinically important protocol deviations. Details of the

criteria for exclusion from the PP population are provided below. An additional determination will be made prior to database lock, based on a review of data accrued during the conduct of the study.

Participants who meet any one of the following criteria will be excluded from the PP:

- Inclusion/exclusion violations
- Subjects that develop withdrawal criteria whilst on the study, but are not withdrawn
- Subjects that receive the incorrect treatment
- Subjects that receive any prohibited medications/foods/fluids as outlined in Sections 5.3, 6.5.2 and 6.5.3 of the protocol;
- Any missed doses of IMP
- Any medical condition that may modify the pharmacokinetic profile of the IMP or compromise the natural immunity of the subject
- End-of-study stool (C1-C3) samples or urine samples (C4) required for assessing the primary endpoint are missing or collected out-of-window

Safety Analysis Population (SAF)

The Safety analysis population will include all participants who receive a dose of study treatment. Participants will be analyzed according to the actual treatment they receive.

Pharmacokinetic Analysis Population (PKP)

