 - If the stop day and month for a concomitant medication is missing, it will default to the day and month of last contact with the participant.
- Missing years will not be imputed.

Note: ATC coding will not be indication/other differentiators (namely route) based, but all ATC available for a drug in the dictionary will be provided.

13 Treatment Compliance and Exposure

Compliance and exposure will be reported for the SAF, mITT and PP analysis sets.

All dosing calculations and summaries will be based on “Dosing Preparation” CRFs pages.

Compliance will be derived as follows:

- $100 \times \{\text{Actual number of doses administered} / \text{expected number of doses that were to be administered}\}$, rounded to the nearest integer using the ROUND() function.

Compliance will be categorised as:

- Compliance = 0% {0 dose administered in C1-C4}
- Compliance = 100% {1 dose administered in C1-C4}

Compliance will be summarised by cohort and compliance level, as well as listed by cohort and subject.

Exposure, in terms of dosing, will be derived as follows:

- Exposure:

{Actual Dose [mg]}

If *Actual Dose* is missing, exposure will be kept as missing.

- Exposure with respect to baseline weight:

{Actual Dose [mg]} / weight [kg], as calculated using the weight measurement at baseline

If *Actual Dose* is missing, exposure will be kept as missing.

14 Efficacy Analyses

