14.3 Supportive Subgroup Analyses for Efficacy Analysis

Analysis set(s):

- Supportive analyses of the primary endpoint will be based on the mITT and PP analysis sets.

Clinical cure rate by subgroup:

If the End of Study Kato-Katz egg count is missing, it will be imputed using the LOCF approach. Subgroup analyses the study will be performed, by the following subgroups:

- Age category (Cohort 4 only)

- Gender
- Severity of infection
- Country

Descriptive statistics of cure rates for each subgroup will be estimated for each cohort.

Cure rate, in terms of proportion of responders, will be summarised by cohort and by infection severity, gender and country and listed by cohort and subject. Estimates of cure rate will be presented graphically in the form of a forest plots presenting point estimates and 95% CIs, by treatment group and subgroup. Forest plot by age group is needed for Cohort 4 only. Cure rates will be presented as percentages, not proportions, i.e. *cure rate* × 100.

For mITT analysis tables will be presented with imputation and without imputation.

15 Safety Analyses

Safety and tolerability assessments:

- Occurrence, nature, severity and outcome of adverse events (AEs),
- Occurrence of treatment-related AEs
- Changes in laboratory safety parameters (hematology, biochemistry, urinalysis) and vital signs (body temperature, blood pressure and pulse rate)

Analysis set(s):

- SAF analysis set.

Safety analyses will be done on the SAF analysis set and according to the as-treated principle. This section includes specifications for summarizing safety endpoints that are common across clinical trials such as AEs, laboratory tests, reactions to the IMP and vital signs.

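### Reaction to administration is tabulated only among dosed children, so a child who refuses before any intake is missing from the acceptability and compliance tables

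*Protocol*

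**What the plan says.** Acceptability, in the sense of ease of administration, is a secondary objective for the ODT and for crushed Biltricide (Protocol Table 1). Its endpoint is the child's reaction at dosing. Protocol 4.2.5 says this is recorded "to describe tolerability as assessed by nurse/site staff for all children enrolled in the study". In Protocol 9.3, enrolled means that consent was signed; no dose is needed.

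SAP Section 15 sets the analysis population: "Safety analyses will be done on the SAF analysis set and according to the as-treated principle". It describes its scope as "safety endpoints that are common across clinical trials such as AEs, laboratory tests, reactions to the IMP and vital signs". SAP 15.6, which handles the reaction data, names no other population. SAP 8.2 defines the set: "The Safety analysis population will include all participants who receive a dose of study treatment". The mITT and PP sets also require a dose, and the SAP treats ITT as equivalent to the safety set.

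SAP Section 13 plans a 0% compliance category for children given no dose, but states: "Compliance and exposure will be reported for the SAF, mITT and PP analysis sets".

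On withdrawal, Protocol 7.2 allows a participant to leave on request of the parent or guardian "or if the child communicates (verbally or opposing resistance) that he/she is unwilling to continue, and without giving a reason". If withdrawal comes before dosing, an End-of-Study visit is done, but otherwise "no attempts will be made to collect additional data. No further evaluations will be performed, except for safety purpose when applicable". SAP Section 7 declares no change from the protocol's planned analyses.

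**The concern.** Refusing the product outright is the most extreme failure of ease of administration. Restricting the table to children who took a dose selects on the outcome being measured.

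In Cohort 1, allocation is open label and made just before dosing (Protocol 6.3.1 and 6.3.2). Refusal at dosing therefore comes after assignment and can depend on the product. The Introduction reports a suggestion that one enantiomer causes much of the bitterness of the commercial formulation, so unequal refusal is plausible, though not shown. The product refused more often would lose its worst cases from the comparison. In the single-arm cohorts, the reported acceptability of the ODT would be too favourable by whatever share of children refused.

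**Working it through.** **Where a child who takes no dose appears**

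- Reaction table (SAP 15, 15.6): absent, because the safety set requires a dose.
- Compliance table (SAP 13): absent. The 0% row is reported on the safety, mITT and PP sets only. All three require a dose, so the row is empty by construction.
- ITT: no help, since SAP 8.2 uses the safety set in its place.
- Screening set (SAP 8.2): present, but no acceptability or compliance table is assigned to it.
- Disposition (SAP 10.1), missed-dose deviations (SAP 8.1) and reasons for exclusion from mITT and PP (SAP 10.2.2): may be present, but refusal is not named as a reason and nothing feeds into the acceptability result.

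**Inputs for size**

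The plan has no figure for acceptability or refusal to reproduce. Planned arm sizes are 150 × 2/3 = 100 (1a) and 150 × 1/3 = 50 (1b). The sizing allows a 5% loss to mITT, 100 × 0.95 = 95 and 50 × 0.95 = 47.5 (stated as 47), all of it for anti-malarial treatment. It therefore implies no refusal rate. All refusal and reaction counts below are assumptions. So is a single combined rate of adverse reactions, since SAP 15.6 only cross-tabulates categories.

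**Shift per refusal**

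Let N children be offered the dose, r refuse, and a proportion p of those dosed react adversely. The safety set shows p. Among all offered, counting refusal as a failure, the rate is [p(N − r) + r]/N = p + (1 − p)r/N. Each refusal therefore adds (1 − p)/N. At p = 20%:

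- group 1b: 0.8/50 = 1.6 percentage points
- group 1a: 0.8/100 = 0.8 percentage points

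**Whole-count illustrations**

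| Assumed reactions and refusals | Safety set, 1a vs 1b | All randomised, 1a vs 1b |
|---|---|---|
| 1a: 20 and 0; 1b: 10 and 0 | 20/100 = 20.0% vs 10/50 = 20.0% | 20.0% vs 20.0% |
| 1a: 20 and 0; 1b: 9 and 5 | 20.0% vs 9/45 = 20.0% | 20.0% vs 14/50 = 28.0% |
| 1a: 20 and 2; 1b: 9 and 5 | 20/98 = 20.4% vs 20.0% | 22/100 = 22.0% vs 28.0% |
| 1a: 20 and 0; 1b: 8 and 3 | 20.0% vs 8/47 = 17.0% | 20.0% vs 11/50 = 22.0% |

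The second row hides 8 points. The last reverses the order of the products.

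Holding the total in 1b at 15 of 50 failures (30.0%), the safety set would show 15/50 = 30.0%, 14/49 = 28.6%, 12/47 = 25.5% or 10/45 = 22.2% if 0, 1, 3 or 5 of the 15 were refusals.

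If both arms refuse in the same proportion f, the difference among all offered is (1 − f) times the safety-set difference. The comparison is then little affected, although both levels are understated.

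**The case against.** The strongest reply has five parts.

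1. **Withdrawal clause.** A reader might infer from 7.2 that a child who resists is always withdrawn and leaves no trace. The text does not support this. It says the participant may withdraw, concerns willingness to continue in the study, and asks for the reason to be obtained and recorded where possible. This stands. It does not rescue the table, because an undosed child is outside the safety set whether withdrawn or not. The statement in 7.2 that data from before withdrawal remain in the analyses does not help either, since SAP Section 15 still selects on dosing.

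2. **Visibility elsewhere.** Disposition is reported by group with enrolled or randomised participants as denominator, and missed doses and exclusion reasons are summarised. Non-dosing can therefore be found by arm. This stands and limits the damage. A reader of the acceptability table would still not see it there.

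3. **Meaning of the protocol wording.** The endpoint is timed at administration, and its reference to all enrolled children could mean all ages, in contrast to the palatability score for ages 5 and 6. Taken literally, enrolled would include consented children never offered a dose. The wording is arguable, and for that reason the denominator should be stated. On neither reading does it call for dropping children who were offered the product and refused.

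4. **Narrow group.** A child who spits or vomits after dosing stays in the analysis (Protocol 6.6), so only zero intake is lost. This stands. The sizing also suggests that undosed children were not expected: five refusals in 1b would leave about 45 × 0.95 = 42.75 for mITT against 47 planned. The upper end of the illustrations is therefore not a forecast.

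5. **eCRF not shown.** The reaction page may already hold a refusal category. That cannot be excluded, but the safety set would still remove the child.

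**Conclusion.** The point holds as an inconsistency of denominator. The SAP measures acceptability only among children who took a dose and plans a zero-dose compliance row that cannot be filled. It declares no departure from a protocol that defines the endpoint for all children enrolled.

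The size depends wholly on refusal counts that the documents do not give. It is nil with no refusals. At an assumed 20% reaction rate it is about 1.6 points per refusal in 1b and 0.8 in 1a, and a few unequal refusals can hide or reverse a difference.

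Two stronger readings should be resisted. A reader might infer that the rule favours the ODT over Biltricide. The documents do not show this: if the commercial product were refused more often, the omission would favour Biltricide. A reader might also infer that the trial's main conclusion is at risk. It is not: acceptability is a descriptive secondary endpoint, no formal comparison is planned, and the primary cure-rate endpoint is unaffected. The change is worth making because it removes selection on the outcome at very little cost.

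**What to change.** - **SAP 15.6:** tabulate the reaction categories plus a separate category for refused or no dose taken, by treatment group. Use all randomised children in Cohort 1, and all children allocated and offered the dose in Cohorts 2 to 4. Keep the safety-set table as supportive.
- **SAP 13:** report compliance on the same set, so that the 0% row can be filled.
- **Consistency:** reconcile this denominator with Protocol Table 1, and amend the statement in SAP Section 7 if any difference from the protocol remains.
- **Data capture:** record refusal at dosing on the reaction eCRF page, if that page has no such category.

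The cost is SAP wording, a changed denominator and possibly one eCRF category. No extra participants or study procedures are needed. The downside is that the reported acceptability figures may become slightly less favourable.

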### **6.5.3 Prohibited Medicines**

As referred to in the exclusion criteria (Section 5.2), administration of PZQ or use of any investigational device within 4 weeks prior to administration of the study intervention (PZQ ODT or Biltricide) and during the entire clinical study is not permitted.

If the administration of a non-permitted concomitant drug becomes necessary during the study, e.g., because of AEs, the participant should be discontinued from the study but only after consultation with the Sponsor. Children who require malaria treatment after receiving study treatment will not be withdrawn from the study, but because some anti-malarial agents (e.g.,

artemisinin derivatives) have activity against *Schistosoma* spp. (Liu et al, 2011), they will be excluded from the primary efficacy analysis.

For children being breastfed, administration of PZQ to nursing mothers is not allowed in the 3 days prior to PZQ ODT administration (see Section 6.5).

The concomitant administration of agents that induce the drug-metabolising enzyme system in the liver (cytochrome P450), such as certain antiepileptics (e.g., carbamazepine or phenytoin), glucocorticosteroids (e.g., dexamethasone) or chloroquine, may lead to reduced plasma levels of PZQ and will not be allowed. The concomitant administration of rifampicin, which is a strong inducer of cytochrome P450, or of other cytochrome P450 inducers, is contraindicated as no therapeutically effective plasma levels of PZQ can be expected in that setting.

Similarly, the concomitant administration of agents that inhibit the cytochrome P450 system, e.g., cimetidine, may lead to increased plasma levels and a prolonged retention period of PZQ and will not be allowed.

As consumption of grapefruit may lead to increased PZQ levels, grapefruits and grapefruit juice products will not be allowed during confinement. In case a participant may have been enrolled and dosed after grapefruit consumption, a protocol deviation will be issued, however participants will not be discontinued from the study and data won't be excluded from the analysis. The Investigator will need to enquire the eventual consumption of grapefruit in the 24 hours before enrolment and ensure that the child eats only the standard meals during confinement. At discharge, he will explain the parent/guardian/legally authorized representative the importance of abstaining from grapefruit consumption until 24 hours after the study intervention administration.

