## Follow-up visits

During the 3 days following their release from the hospital, participants will be monitored by the nurses in the health areas and/or by the community agents of the different localities for potential AEs. If an AE is observed, the nurse/community agent will need to inform the medical team in charge of the study for the necessary follow-up.

At the End-of-Study visit (between Days 17 and 21), participants from Cohorts 1, 2, and 3 will be asked to provide two stool samples (the first one will be collected within the 17 to 21 day window and the second one within a maximum of 5 days following collection of the 1st sample) and one urine sample (about 10 mL) for analysis using the Kato-Katz and POC-CCA tests respectively.

Cohort 4 participants will be asked to provide three urine samples (about 10 mL each), within 5 days, for analysis by the filtration method at the End of Study Visit between Days 17 and 21, as well as the Extended Follow-up Visit (between Day 35 and 40).

CCI

The following tests and information gathering will be also performed:

- Vital signs in supine position (see Section 8.2.3)
- Complete physical examination (see Section 8.2.2)

If a participant withdraws prematurely from the study, every effort will be made to undertake a final examination visit as soon as possible and perform all procedures associated with the End-of-Study visit.

Any ongoing medically relevant abnormal findings at the End-of-Study visit, will be followed up until resolution or stabilization (according to [Appendix 3](#))

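### Protocol Section 7.2 ends evaluation at withdrawal and keeps later safety data out of the database, in conflict with Section 8, Section 8.3.1 and the SAP

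*Protocol*

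**What the plan says.** **Protocol Section 7.2.** Once a participant withdraws, "no further evaluations should be performed, and no attempts should be made to collect additional data". Safety data are excepted, "which should still be collected if possible, but not captured in the database". Data from before "withdrawal will still be included in the efficacy and safety analysis". If withdrawal is for a treatment-limiting AE, its outcome must be thoroughly documented. The only End-of-Study visit this section orders is for children who leave before dosing: "If a participant withdraws prior to administration of the study treatment, the End-of-Study visit will be performed".

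**Protocol Section 8, Follow-up visits.** "If a participant withdraws prematurely from the study, every effort will be made to undertake a final examination visit" as soon as possible, and to "perform all procedures associated with the End-of-Study visit".

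**Protocol Section 8.3.1.** AEs go into the database from the Screening visit to the End-of-Study visit, with no exception for withdrawn children. SAEs judged related are recorded and reported whenever they occur.

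**Protocol Section 6.5.3.** If a non-permitted drug becomes necessary, for example because of an AE, "the participant should be discontinued from the study but only after consultation with the Sponsor". Children who need malaria treatment after dosing stay in the study but leave the primary efficacy analysis.

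**SAP.** Section 10.1 counts as completers only those whose End of Study visit was not due to early withdrawal, so it expects some such visits in the data. Section 15.3 allows the end-of-treatment laboratory value to come from an early-withdrawal sample.

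**The concern.** The study gives one dose, and Section 7.1 (discontinuation of study intervention) is marked not applicable. Withdrawal after dosing therefore spares the child no further study drug. What it ends is observation. Section 7.2 tells a site to seek nothing more, apart from safety data that it must leave out of the database. Section 8 tells the same site to try for a full final visit. Both use the same verb for the child who leaves, so they are not cleanly separated as self-withdrawal versus withdrawal by the investigator.

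Two things are at stake. A dosed child without a follow-up sample counts as not cured in the imputed mITT analysis (Protocol Section 9.4.1; SAP Section 14.1.1), so an avoidable missing sample lowers the estimated cure rate. AEs that staff learn of after withdrawal would not reach the safety tables. Because Section 6.5.3 offers a route out of the study prompted by AEs, the missing safety data need not be a random subset. Sites may also act differently depending on which section they read.

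**Working it through.** **The plan's own figure.** Table 5 (Protocol Section 9.2) gives group 1a, mITT n = 95. For 76/95 = 80.0%, the exact Clopper-Pearson lower limit is 70.5% and the precision 9.5 points. Both reproduce, as do the other rows of Table 5 to within 0.1 point. No figure in the plan is in dispute.

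**The instructions side by side, for a dosed child withdrawn before Day 17.**

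| Question | Section 7.2 | Other text |
|---|---|---|
| Final visit? | None ordered after dosing; no attempts to collect more data | Section 8: every effort, all End-of-Study procedures |
| Later AEs in the database? | No | Section 8.3.1: yes, up to End-of-Study |
| Early-withdrawal data in the outputs? | None would exist | SAP 10.1 and 15.3 expect them |

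**Effect on the imputed cure rate.** Inputs: n = 95 (Section 9.2); a missing outcome is set to not cured (Section 9.4.1, SAP 14.1.1). The number withdrawn, k, and the 80% cure probability are assumptions, since the documents give no post-dose withdrawal rate.

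- Largest effect per child, if that child was in fact cured: 1/95 = 1.05 points.
- Average effect per child if 80% would have been cured: 0.8/95 = 0.84 point.
- Illustration, with about 80% cured among the 95 − k children assessed:

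| k | Imputed cure rate | Lower 95% limit |
|---|---|---|
| 0 | 76/95 = 80.0% | 70.5% |
| 2 | 74/95 = 77.9% | 68.2% |
| 5 | 72/95 = 75.8% | 65.9% |

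At k = 5 the shift is 80.0 − 75.8 = 4.2 points, against a planned precision of 9.5. In the tables without imputation the child is left out and the rate stays near 80% (72/90 = 80.0% at k = 5).

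**Effect on AE proportions.** With N = 100 dosed in group 1a, each withdrawn child whose first AE comes after withdrawal lowers the recorded proportion by 1/100 = 1 point. Five withdrawn children therefore lower it by between 0 and 5 points. The documents give no rate of late AEs to narrow this. They do point to the low end: Sections 6.9 and 8.2.1 expect drug-related AEs within about 12 hours of dosing, which is during confinement.

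**The case against.** A fair defence has several parts.

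- **Section 8 is best-effort.** It can be read as one exit visit, with nothing sought after it. That softens the conflict but does not remove it: Section 7.2 orders no exit visit after dosing, and the database rule still contradicts Section 8.3.1. An exit visit held as soon as possible may also fall before Day 17, so following Section 8 would not by itself secure the primary outcome.
- **Some losses cannot be avoided.** Where consent to data collection is withdrawn, stopping is right. Children who cannot be reached are classed as withdrawn (Section 7.3), and no wording recovers their samples. This stands, and it confines the point to children who are reachable and whose families agree.
- **The imputation is pre-specified and conservative.** The SAP also tabulates mITT without imputation, and no hypothesis test or formal comparison depends on the result. This stands, but those tables omit the children and do not recover their outcomes.
- **Section 6.5.3 is not automatic.** Discontinuation follows only after consultation with the Sponsor. This stands. The text leaves open whether such a discontinuation also ends data collection.

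A reader might infer that all safety data of withdrawn children are kept out of the database. The documents do not support that: earlier data are analysed, so an AE that prompts withdrawal is included, and SAP Section 15.1.1 plans a listing of TEAEs leading to withdrawal. A reader might also infer that outcomes are certain to be lost and AEs materially undercounted. That too is unsupported, because it depends on which section a site follows and on a withdrawal rate that is not given.

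**Conclusion.** The conflict between Section 7.2 on one side and Section 8, Section 8.3.1 and SAP Sections 10.1 and 15.3 on the other is real and should be resolved. It is an internal inconsistency with a conditional cost. If Section 7.2 is followed, each reachable, consenting child withdrawn after dosing costs the imputed group 1a cure rate at most 1.05 points, or about 0.8 point on the 80% assumption. AEs arising after withdrawal are missing from the safety tables. If Section 8 is followed, much of this does not occur, so uneven handling between sites is itself part of the problem. The total effect cannot be stated, because the number of such children is unknown. The AE undercount is probably small, given the expected 12-hour timing and the reporting of related SAEs at any time.

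**What to change.** - Reconcile Sections 7.2, 8 and 8.3.1 so that one rule governs visits, samples and database entry after withdrawal.
- Separate withdrawal of consent to data collection from every other withdrawal after dosing. For the first, stop collecting. For the others, where the family agrees, obtain the stool or urine samples within the Day 17 to 21 window and AE information to the End-of-Study visit, and enter both in the database.
- State in Section 6.5.3 whether discontinuation from the study ends data collection. If data collection continues, prohibited-medication use can be handled through the existing analysis sets: SAP Section 8.2 already excludes such children from the per-protocol population.

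The cost is protocol wording, use of existing eCRF pages and a few extra follow-up contacts. No dose or treatment rule changes.
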